For the HANSE trial, 5,000 participants aged 55-79y who meet the NELSON and/or PLCO_{M2012} 6 year risk >1.58% selection criteria will be included. Participants will undergo baseline and 1-year screening under defined conditions using low-dose computed tomography in three specialized lung cancer centers in northern Germany.

Standardized and quality-assured image analysis will be conducted using state-of-the-art artificial intelligence (AI)-based detection and nodule measurement software (AVIEW, Coreline Soft Company Ltd., South Korea) to support the radiologist. CT assessment of lung nodules will be done according to LungRADS 1.1 criteria, as well as volume doubling time according to the European position statement on lung cancer screening (14). Additionally, this trial integrates different recruiting strategies, a smoking cessation counselling program, includes a cost-effectiveness modelling, cardiovascular and lung comorbidity assessment, different lung nodule management strategies (Lung RADS 1.1. vs. PanCan vs. AI) and explores blood-based biomarkers in positive LDCT cases.

An additional objective of the HANSE study is to provide evidence for the potential of low dose CT in the diagnosis of diseases other than lung cancer, such as emphysema, but also cardiovascular diseases, which to date has only been suggested by retrospective analyses of LDCT studies (15, 16). Low dose CT does allow to examine the coronary calcium score (Agatston score (17)), indicative of the coronary plaque status which has shown to correlate with the rate of future myocardial infarction, stroke and death due to cardiovascular disease (18). The trial will assess whether reporting of the score may have consequences in individuals with a positive

coronary calcium score seeking specialist consultation and initiating preventive cardio-vascular therapy.

The trial will further encompass a smoking cessation program and smoking cessation rate under the different experimental settings will be determined at 1-year follow-up. Specifically, the consequences on smoking status will be compared between the non-reporting group, the calcium score reporting group, the emphysema score reporting group vs. the non-reporting group in order to document a potential impact of reporting.

Additionally, this design feature allows to analyse long-term smoking cessation rates and mortality in a follow-up study at year 5 and 10 (not part of this funding period).

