2.2 Secondary Objective(s) & Hypothesis(es)

Key-Secondary Objectives:

The PLCO_{M2012} model and the NELSON inclusion method will be compared

(ii) secondarily to the primary objective regarding the following hierarchically ordered key-secondary endpoints:

1. Proportion of individuals selected for screening
2. Proportion of lung cancers detected
3. Sensitivity and specificity of the scores in cancer detection

Secondary Objectives:

The main secondary objectives of this trial is to document that:

1. Reporting of the coronary artery calcium score from low dose computed tomography (LDCT) data will lead to an increase in the rate of preventive cardiovascular treatments and reduced cardiovascular mortality.

Additional objectives are to show that:

1. Effective smoking cessation counselling is implemented as part of the screening program (urine cotinine check in quitters).
2. CT derived information on tobacco related lung destruction, such as emphysema, may influence the smoking cessation rate.
3. Structured reporting of clinically relevant non-cardiac incidental findings, e.g., emphysema or lung fibrosis, will lead to early detection and improved management of diseases.
4. Adding the PanCan algorithm/AI to the LungRads1.1 algorithm for nodule management increases the efficiency.
5. Assessment of various blood-based or exhalation-based biomarkers may provide additional translational information in positive LDCT cases with subsequent biopsy, which may have an impact on the effectiveness of the LDCT test.
6. Cost effectiveness analysis on recruiting strategies, risk models used, effectiveness on smoking cessation and cardiovascular mortality is implemented.

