4.2 Outcomes

Primary endpoints:

1. Proportion of lung cancers detected with different risk models

To address the suitability of different inclusion methods for identifying the high-risk population for screening, the PLCO_M2012 model and the NELSON inclusion criteria will be compared primarily for the positive predictive value of lung cancers detected within the study population after 2 screening rounds.

Key-Secondary endpoints:

Additionally, the PLCO_M2012 model and the NELSON inclusion criteria will be compared in a hierarchical order regarding the key secondary endpoints:

1. Proportion of individuals selected for screening within the high-risk study population
2. Proportion of lung cancers detected with different inclusion methods (NELSON vs. PLCO) within the overall study population after 5 years
3. Proportion of lung cancers detected within the high-risk population
4. Sensitivity within the overall population after 5 years.

5. Specificity within the overall population after 5 years.

Secondary endpoints:

6. **Rate of initiation of cardiovascular treatments** (in particular lipid-lowering) in the calcium score reporting group vs. the non-reporting group after year 1 of study.
7. **Efficiency of nodule management algorithms:** Based on the two alternative management algorithms (LungRads1.1 alone or LungRads1.1 + PanCan/AI) participants are sorted into three management groups: (a) next surveillance scan, (b) early recall scan, or (c) diagnostic evaluation recommended. For one algorithm to be more efficient, the following criteria must both be fulfilled
 - i. The number of participants without cancer sorted in the category (a) is higher AND
 - ii. The number of participants with lung cancer sorted into category (b) or (c) is higher.
8. **Success of screening program.** Based on all individuals enrolled. Definition of success is calculated using:
 - a. Response rate (1. Respondents to questionnaire / invitation: those who send their smoking history & other relevant data; 2. among the above respondents, those who are eligible by one of the two criteria, or both; 3. those who are eligible, and actually take part in the screening), number of drop-outs, effectiveness of patient recruitment via mailings vs. GPs referrals (individual response rates)
 - b. Reliability of PLCO risk scoring (self-reported vs. on site assessment)

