For the HANSE study the calibrated threshold for the PLCO 5 year risk score of 1,314% was converted to a 6year threshold of 1,58% , because the original PLCO risk score calculates the 6year risk and thus the original calculators by Tammemägi et al. can be used for the HANSE study (13).For this conversion linearity between year 5 and 6 was assumed.

(ii) Sample size for the evaluation of **initiation of cardiovascular therapy** within 1 year after randomization has been calculated using Chi-Square Test and two-sided type-I-error rate of 5% based on the results of the ITALUNG study (15,16), where for 44% of all patients coronary artery calcification (CAC) was detected. In the ITALUNG study, 63% of patients with CAC were on cardiovascular treatment without receiving results of their low dose CT screening. For this study, where the patients are randomized to either reporting or non-reporting of CT screening results, we conservatively assume that the non-reporting group shows a rate of cardiovascular treatment of 68%. In contrast, as an effect of reporting the screening results, we assume that in the reporting group 73% of patients receive cardiovascular treatment, so the effect of reporting the CT results is assumed to be an increase of 5 percentage points in the cardiovascular treatment rate. Acknowledging that only 44% of all patients are assumed to show CAC on low dose CT, the expected difference between the reporting and non-reporting group is $(73\% - 68\%) * 44\% = 2.2\%$. Equivalently, the assumed rate ratio between the reporting and non-reporting group is $(73\% * 44\%) / (68\% * 44\%) = 1.07$. With 2,500 patients randomized to each arm and using a Chi-Square Test with a two-sided type-I-error rate of 5% for testing the null-hypothesis of no difference between the groups, the statistical power is 97%.

(iii) To evaluate the power of potential **longitudinal follow-up** studies based on this screening trial, the power for the 10 year mortality endpoint has been calculated based on the results of the NELSON study using a Chi-Square Test with a two-sided type-I-error rate of 5% for testing the null-hypothesis of no difference in 10-year cardiovascular mortality rates between the

reporting and non-reporting groups. In line with the results of the NELSON study, we assume a 10 year cardiovascular mortality rate in the non-reporting group of 2.7%.

[figure not shown]

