- Non-qualifying subjects (who did not meet the NELSON inclusion criteria or PLCO criteria) will be asked to volunteer by contributing long-term outcome data informing of the development of lung cancer or death from lung cancer. In addition NELSON and PLCO non-qualified subjects with a smoking history, who volunteered to participate in the HANSE study, will be contacted via mail after 5 years to inquire if they developed lung cancer in the time between their recruitment and present. Non-responders will be followed by local cancer registries and by phone.

2. **LDCT - 1. Screening round**

- **Lung function test:** All included participants will receive a lung function test prior to undergoing LDCT.
- **Cardiovascular health:** All participants will be questioned whether they receive treatment for any cardiovascular conditions. Blood pressure, heart rate and BMI data (height and weight) will be obtained.
- Assessment of current **COPD treatment medication.**
- **Randomization:** Subjects included in the screening study will be randomized prior to receiving the initial LDCT scan. Randomization will not affect the procedure and the schedule of the cancer screening process but only determine the allocation of the participants of the coronary calcium score and emphysema score to the reporting and the non-reporting group. Randomization ratio of 1:1 and a 2-factorial design ($\frac{1}{4}$ calcium score only; $\frac{1}{4}$ emphysema score only, $\frac{1}{4}$ both; $\frac{1}{4}$ none) will provide equally sized groups of patients in both groups including age (5 year groups) and sex stratification .

Lung LDCT assessment:

- **Standardized and quality-assured image analysis** will be conducted using state-of-the-art artificial intelligence (AI)-based detection and nodule measurement software (Coreline) to support the radiologist. CT assessment of lung nodules will be performed according to LungRADS 1.1 criteria (see Appendix), as well as volume doubling time according to the European position statement on lung cancer screening (14).
- Inspection of **lungs for nodules** will be carried out for all subjects, independent of the assigned groups (reporting or non-reporting).
- An independent 2nd read by an additional radiologist using the same reading software algorithm will be performed.
- Subjects with no nodules or those of LungRADS grades 1, 2, 3, 4a will be scheduled for follow-up scans at intervals according to LungRADS schedule (see Appendix).

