- Findings categorized as LungRADS Cat. 4b or 4X nodules will be presented to the local Multidisciplinary Tumor Board (MDT) for further assessment and treatment decisions in the clinical routine workflow.
- **Emphysema** severity as a measure for tobacco related lung destruction will be quantitatively assessed on the LDCT images using the fully automated artificial intelligence (AI)-based algorithm of the Coreline software (Coreline, Seoul South Korea). The data will either be reported to study participants and treating physicians or not according to the allocation of the individual to the two randomized experimental groups.
- **Coronary calcium scores** (Agatston score) will be assessed using the fully automated artificial intelligence (AI)-based algorithm of the Coreline software (Coreline, Seoul South Korea). However, only the reporting group will receive the results of the score, together with an explanation of potential consequences of these findings for their cardiovascular health and with recommendation to seek specific consultation with their general practitioner or specialist. In this group a report is sent to the participants' GP.
- The LDCT image data, the coronary calcium score and % emphysema of the non-reporting group will remain confidential and will be stored for further assessment at year 1 (follow-up CT screen) and for evaluation of endpoints at year 5 and 10 (not part of this funding period).
- Apart from the randomized reporting of coronary artery calcium score and % emphysema **clinically relevant incidental findings** will be categorized in emergent (within 1-30 days), timely (within 1-6 months) or regular (>6 months) follow up. They will always be included in the CT report for the study participants.

- For emergent findings the study participant will be contacted directly by the local study team.
- Clinically non-relevant CT findings (i.e. liver or kidney cysts) not requiring physician consultation will not be included in the report.

Smoking cessation program:

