smoking cessation program. A team of clinical and health economic experts will define the detailed structure of the model.

- **Outcome analyses:** For each screening scenario, a Monte Carlo simulation (MCS) with 1,000 iterations will be performed to estimate expected outcomes and MSC-based confidence intervals. Primary outcomes of the analysis are long-term all-cause mortality, additional costs per quality-adjusted life year (QALY) gained, per life year (LY) gained or per death averted. Efficiency frontiers will be constructed for each primary outcome to identify efficient screening scenarios and calculate the incremental cost-effectiveness of these scenarios. The impact of variations in the values of key input parameters (adherence to screening, smoking cessation etc.) on model outcomes will be tested in sensitivity analyses.

Consequences of screening:

- All screened individuals will ask to participate in a 'Consequences of Screening' survey in order to evaluate their emotional and psychological condition during the screening process. Survey will be based on the psychological consequences questionnaire, adapted for lung cancer screening (19).
- In addition, the patient questionnaire will evaluate the socioeconomic background, smoking cessation, lung and cardiovascular health.
- The exact questions of the questionnaire will be determined before the study start and included in the appendix of the protocol.
- GP contact information is recorded.
- Current medication is recorded.

3. LDCT 1 year - 2. Screening round

Timing of the follow-up chest CT according to LungRADS 1.1 schedule.

Chest LDCT scan procedure and image analysis as in the 1st screening round.

- **Lung LDCT assessment:** Assessment of newly identified lung nodules will be done according to LungRADS 1.1 criteria. Follow-up radiographic assessment of solid nodules will be based upon volume doubling time (VDT) as a key driver for recommendations on further course of action.
- **Lung function test:** All included participants will receive a lung function test prior to undergoing LDCT.

- **Cardiovascular health:** All participants will be questioned whether they initiated treatment for any cardiovascular conditions during the study. Blood pressure, heart rate, and BMI data will be obtained.
- Additionally, the study is designed to analyze cardiovascular events and mortality in a follow-up study at year 5 and 10 (not part of the current funding period).

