- **Assessment of smoking status:** Success of the smoking cessation program will be evaluated using a questionnaire, combined with a urine cotinine check (in quitters).
- **Initiation of COPD treatment:** Assessment of COPD treatment initiation during the study.
- **Consequences of screening:** Questionnaire 'Consequences of Screening' as above.

2. Evaluation

Lung cancer screening:

- The percentage of subjects receiving an adequate low-dose CT scan according to DRG guidelines will be assessed.
- For all included participants, detection rate of lung cancers will be evaluated and categorized according to LungRADS 1.1 categories.
- Detected (proven by histopathology) lung cancers will be categorized whether they were predicted by PLCO or NELSON or both. Statistical analysis will reveal potential advantages of either risk scoring methodology.
- A retrospective analysis will compare this algorithm to the PanCan nodule algorithm vs. AI for management efficiency. Based on the two alternative management algorithms patients are sorted into three management groups: (a) next surveillance scan, (b) early recall scan, or (c) diagnostic evaluation recommended. For one algorithm to be more efficient, the following criteria must both be fulfilled
 - The number of patients without lung cancer sorted in the category (a) is higher AND
 - The number of patients with lung cancer sorted into category (b) or (c) is higher.

Coronary calcium score / cardio-vascular treatment initiation:

- At the 1-year follow-up visit, the rate of initiation of cardiovascular treatment (in particular lipid-lowering) will be determined, together with BMI, and blood pressure data. Data for the calcium score reporting group will be compared to those of the non-reporting group.

Smoking cessation:

- Success of smoking cessation counseling will be based on the number of participants quitting (% quitters) within study period.
- Allocation of the participants to the different experimental groups will allow determining the influence of 'reporting' of prognostic markers (percent emphysema and coronary calcium score) on smoking cessation.

All methods will be performed according to study site SOPs.

CT analysis software (Coreline) specifications:

1. Viewer function

- LCS (Lung Cancer Screening) viewer functions

- Image display with axial, sagittal and coronal images and 3D rendering.
- Virtual slice thickness control display function for MPR (Multi-Planar Reformat) images.

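### The cardiovascular endpoint counts treatment starts, but its stated 97% power belongs to the proportion on treatment, and stops are not counted

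*Protocol*

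**What the plan says.** The protocol describes the cardiovascular question in several places.

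- Objective (2.2): reporting the calcium score "will lead to an increase in the rate of preventive cardiovascular treatments and reduced cardiovascular mortality".
- Rationale (1.2): the interest is in people with a positive "coronary calcium score seeking specialist consultation and initiating preventive cardio-vascular therapy".
- Endpoint (synopsis, 4.2, 5.1.2): the rate of initiation, "in the calcium score reporting group vs. the non-reporting group after year 1 of study".
- First screening round (6.1.2): "All participants will be questioned whether they receive treatment for any cardiovascular conditions". Current medication is also recorded in this round.
- One-year visit (6.1.2): "All participants will be questioned whether they initiated treatment for any cardiovascular conditions during the study". The evaluation paragraph then says that "the rate of initiation of cardiovascular treatment (in particular lipid-lowering) will be determined, together with BMI, and blood pressure data".
- Who learns the score (6.1.2): "only the reporting group will receive the results of the score". Nothing restricts the report to positive scores, and randomisation precedes the scan.
- Sizing (5.3 (ii)): the item is labelled as therapy initiation. It starts from 63% of participants with calcification already on treatment in an earlier screening trial and assumes 68% without reporting. With reporting, "we assume that in the reporting group 73% of patients receive cardiovascular treatment". It expects calcification in 44%, derives a difference of 2.2 points, and states 97% power with 2,500 per arm (chi-square test, two-sided 5%).
- Status (5.2.2): all secondary parameters are explorative.

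**The concern.** Two quantities share one name. The endpoint and the one-year question concern events: did a participant start treatment during the year? The sizing and the baseline question concern a state: is a participant on treatment? They differ in three ways. Someone treated at baseline counts towards the on-treatment proportion but cannot start. A start rate over one year will generally be far from 68%. Someone who stops lowers the on-treatment proportion and leaves the start rate untouched.

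The stated power therefore cannot be relied on for the endpoint as written. And if reporting prompts starts in some participants and stops in others, the planned comparison shows only the first. This is the trial's main secondary objective, and the sizing section concludes that the study is well powered to evaluate cardiovascular benefit.

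**Working it through.** **Inputs from 5.3 (ii):** 68% and 73% on treatment among those with calcification; calcification in 44%; 2,500 per arm; two-sided 5%. **Not given, so assumed over a range:** the treated share among participants without calcification (q), the background one-year start rate (s), and any stopping rate.

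Formula: power = Φ{ [|p1 − p2| − 1.96·√(2p̄(1 − p̄)/n)] / √([p1(1 − p1) + p2(1 − p2)]/n) }, where p̄ is the mean of p1 and p2.

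1. **The plan's own figure.** With p1 = 0.68, p2 = 0.73, n = 2,500: (0.05 − 1.96 × 0.01290)/0.01288 = 1.92, so power is 97.3% (97.0% with continuity correction). The stated 97% is reproduced, from on-treatment proportions applied to every participant in each arm.

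2. **Could 68% be a start rate?** If 63% of comparable people with calcification are already treated, at most 37% of them can start, so 68% is impossible as a share of all people with calcification. As a share of the untreated it is arithmetically possible, but the base would then be about 0.44 × 0.37 × 2,500 = 407 per arm, not 2,500.

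3. **With the plan's own dilution.** 0.44 × 0.68 = 29.92% and 0.44 × 0.73 = 32.12%, a difference of 2.2 points. Then (0.022 − 1.96 × 0.01308)/0.01308 = −0.28, so power is 39.0%. Restricting the comparison to participants with calcification (0.44 × 2,500 = 1,100 per arm, 68% versus 73%) gives 73.0%.

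4. **On-treatment status in all randomised participants.** Control rate 0.44 × 0.68 + 0.56q; reporting rate 0.44 × 0.73 + 0.56q.

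| q (assumed) | Control | Reporting | Power, 2,500 per arm | n per arm for 80% |
|---|---|---|---|---|
| 0 | 29.9% | 32.1% | 39% | 6,939 |
| 0.20 | 41.1% | 43.3% | 35% | 7,911 |
| 0.40 | 52.3% | 54.5% | 34% | 8,070 |
| 0.68 | 68.0% | 70.2% | 39% | 6,924 |

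5. **Starts.** The protocol gives no start rate. If the whole 2.2-point gain came through extra starts, with all 2,500 per arm in the denominator, power would be about 99% for s = 2%, 90% for 5%, 70% for 10% and 48% for 20%. The 2.2 points are an on-treatment difference, so using them here is an assumption.

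6. **How much stopping would matter.** The planned gain is 0.05 × 0.44 × 2,500 = 55 participants. About 0.56 × 2,500 = 1,400 in the reporting arm would have no calcification. Extra stopping among the treated ones that offsets the gain exactly is 55/(1,400q): 19.6% for q = 0.20, 9.8% for q = 0.40, 6.5% for q = 0.60. These are break-even values, not estimates.

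**The case against.** Initiation was a deliberate choice. The rationale is worded that way, and the limitations text explains that it was selected because the 36-month horizon rules out ten-year cardiovascular mortality. The objective can be read as a start rate. On that view the sizing is the outlier, and correcting it alone would remove the contradiction. This stands: the endpoint need not be replaced, but the two must be reconciled.

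All secondary parameters are explorative, so no confirmatory claim depends on this one. That also stands and limits the consequence.

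Medication at one year may be collected after all. The round-one medication item sits in the list under the questionnaire on consequences of screening, and round two repeats that questionnaire by cross-reference. The questionnaires are separate documents and are not at hand. So one-year medication data cannot be ruled out, but the stated endpoint does not use them.

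A reader might go further and infer that the trial will report a null net effect as an increase. The documents do not support that. They give no stopping rate and no treated share among people without calcification, and they do not say what a zero-score report contains; scores go out with an explanation, advice to consult a physician and a report to the general practitioner. A reader might also infer recall bias towards starts, or a distorted cost-effectiveness model. Neither is shown. The baseline item is also a question put to participants, and the initiation rate is not named as an input to a model whose detailed structure is still to be defined.

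**Conclusion.** The mismatch is in the text and needs no assumption: the endpoint and the one-year question count starts, while the sizing and the baseline question concern being on treatment. The stated 97% reproduces from on-treatment rates of 68% and 73% in all 2,500 per arm. It is therefore not the power of the endpoint as written, and it omits the 44% dilution from the same paragraph. With the diluted rates it is about 39%. For on-treatment status in all randomised participants it is 34–39% over an assumed q of 0 to 0.68.

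That stops go uncounted is a real gap in the stated endpoint. Its effect is conditional: if reporting leads some treated participants to stop, a rise in starts would overstate the net change in treatment. Whether this happens, and how often, cannot be judged from the protocol. The point deserves correction, but the explorative status of the endpoint keeps it below the issues that affect the primary comparison.

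**What to change.** 1. At the existing one-year visit, repeat in both arms the round-one question on being under cardiovascular treatment and the current-medication record. Derive starts and stops by comparing the two visits.
2. Report by calcium-reporting allocation: the proportion on preventive treatment at one year, starts among those untreated at baseline, and stops among those treated at baseline.
3. State which of these is the sized endpoint, use the same term in the objective, 4.2, 5.1.2, 5.3 and 6.1.2, and restate its power. For on-treatment status in all randomised participants it is about 34–39% at 2,500 per arm; 80% would need about 6,900 to 8,100 per arm. These figures are unadjusted. Adjusting for baseline treatment status should help, but the protocol gives nothing from which to quantify it. For starts, state the assumed background rate and denominator.
4. Revise the conclusion in 5.3 that the study is well powered for the cardiovascular question.

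The cost is one repeated eCRF page, changes of wording, and a less favourable stated power. The change concerns measurement and reporting only; starts remain available as an outcome, and nobody's care is affected.
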